5.2.3 Concomitant medication date imputation

Missing concomitant medication dates will be imputed similar as to AE dates.

5.2.3.1 Other imputations

NA

5.2.4 Visit windows

When visit windows are used, all visits will be re-aligned, i.e., they will be mapped into one of the visit windows. E.g., if the Day 4 visit of a patient is delayed and occurs on Day 7, say, it will be re-aligned to visit window Day 8. In the case of major deviations from the visit schedule, or due to unscheduled visits, several assessments of a patient may fall in a particular visit window (either scheduled or unscheduled). Statistical approaches to handle multiple assessments in a given visit window are specified below.

- Of note, patients are allowed to have gaps in visits. All data collected will be displayed in listings.
- The following rules are used to determine the window for other visits post baseline:
 - “Lower limit” = “upper limit of prior applicable visit” + 1.
 - “Upper limit” = “target day of current visit” + integer part of (“target day of next applicable visit” – “target day of current visit”)/2
 - No upper limit for Day 29 visit to include all assessments

For assessments that are scheduled to be performed only once on a day, [Table 5-8](#) describes the analysis windows mapping to visits (not just scheduled visits) based on study days alone. For the assessments that may be performed on multiple timepoints on a day, [Table 5-9](#) describes the analysis windows mapping to visits based on study day and time. Repeat and/or unscheduled visits (which will be numbered in the database according to new NCDS standards) will be mapped for analysis purposes in the same way. If there are multiple measurements within an analysis window, the conventions defined in [Table 5-10](#) will be used to determine the appropriate measurement to be selected for analysis.

The mapped visits will be used in the by visit analyses. However, the listings will show all collected data regardless of used in the by visit analyses.

Table 5-8 Analysis visit windows based on study days alone

Analysis Visit	Target Day	Analysis visit window for assessment group					
		ECG	Body weight ¹	Body height/Head circumference/body weight ²	INR/LDH	AAG	
Baseline	1	Up to Day 1	Up to Day 1	Up to Day 1	Up to Day 1	Up to Day 1	
Day 2	2	Day 2	Day 2-15	NA	NA	Day 2	
Day 3	3	Day 3	NA	NA	NA	Day 3 and above	
Day 4	4	Day 4 to Day 16	NA	NA	NA	NA	
Day 6	6	NA	NA	NA	NA	NA	
Day 8	8	NA	NA	NA	Day 2 and above	NA	
Day 15	15	NA	NA	NA	NA	NA	
Day 22	22	NA	NA	NA	NA	NA	
Day 29/ End of study	29	Day 17 and above	Day 16 and above	Day 2 and above	NA	NA	

¹ Cohorts 1-3 ² Cohorts 4-5

Table 5-9 Analysis visit windows based on study day and time

Target visit	Target timepoint	Blood smear	PK (Cohorts 1 to 3)	PK (Cohorts 4-5)	Neurological/severe malaria assessment/ body temperature/blood pressure/pulse	Blood chemistry/hematology Point of Care device	Urinalysis
Baseline	0 hrs	up to 0 hrs	up to 0 hrs	NA	up to 0 hrs	up to 0 hrs	up to 0 hrs
Day 1	2 m	NA	>0 – 6m	>0 – 31 min	NA	NA	NA
	10 m	NA	>6m – 35 m	NA	NA	NA	NA
	30 m	NA	NA	NA	>0 – 3.25 hrs ¹	NA	NA
	1 hrs	>0 - 1.5 hrs	>35 m- 2.5 hrs	>31 min- 12.5 hrs	NA	NA	NA
	2 hrs	>1.5 – 3 hrs	NA	NA	NA	NA	NA
	4 hrs	>3 – 5 hrs	>2.5 – 8 hrs	NA	NA	NA	NA
	6 hrs	>5 - 9 hrs	NA	NA	>3.25-9 hrs	> 0 – 9 hrs ²	NA
	12 hrs	>9 - 15 hrs	>8- 18 hrs	NA	>9 - 15 hrs	>9 – 18 hrs	NA
	18 hrs	>15 - 21 hrs	NA	NA	>15 - 21 hrs	NA	NA
Day 2	24 hrs	>21 – 27 hrs	>18 – 24 hrs 1 min	>12.5 hrs – 36 hrs	>21 – 30 hrs	>18 -30 hrs	>0 – 30 hrs
	24 hrs 2 min	NA	>24 hrs 1 min-24 hrs 31 min	NA	NA	NA	NA
	25 hrs	NA	>24 hrs 31 min– 30.5 hrs	NA	NA	NA	NA
	30 hrs	>27 – 33 hrs	NA	NA	NA	NA	NA
	36 hrs	>33 – 39 hrs	>30.5 –42 hrs	NA	>30 – 42 hrs	>30 – 42 hrs	>30 -42 hrs

Target visit	Target timepoint	Blood smear	PK (Cohorts 1 to 3)	PK (Cohorts 4-5)	Neurological/severe malaria assessment/ body temperature/blood pressure/pulse	Blood chemistry/hematology Point of Care device	Urinalysis
	42 hrs	>39- 45 hrs	NA	NA	NA	NA	NA
Day 3 e	48 hrs	>45 – 60 hrs	m>42 – 48 hrs 1 min	>36 hrs	>42 -60 hrs	>42 -60 hrs	>42 – 60 hrs
	48 hrs 2 min	NA	>48 hrs 1 min – 48 hrs 31 min	NA	NA	NA	NA
	49 hrs	NA	>48 hrs 31 min – 54.5 hrs	NA	NA	NA	NA
	60 hrs	NA	>54.5 – 66 hrs	NA	NA	NA	NA
Day 4	72 hrs	>60 hrs to Day 5	>66 – 96 hrs	NA	>60 hrs to Day 5	>60 hrs to Day 5	>60 hrs to Day 5
Day 6	120 hrs	Day 6 – 7	>96 hrs – 144 hrs	NA	Day 6 – 7	Day 6 – 7	Day 6 -7
Day 8	168 hrs	Day 8 - 11	>144 hrs	NA	Day 8 - 11	Day 8 – 11	Day 8 -11
Day 15	336 hrs	Day 12 - 18	NA	NA	Day 12 - 18	Day 12 – 18	Day 12 - 18
Day 22	504 hrs	Day 19 - 25	NA	NA	Day 19 - 25	Day 19 - 25	Day 19 - 25
Day 29	672 hrs	Day 26 and above	NA	NA	Day 26 and above	Day 26 and above	Day 26 and above

¹ for body temperature and vital signs; ² for Point of Care device

Table 5-10 Rules for flagging variables

Timing of measurement	Type of data	Rule
Baseline	All data	The last measurement made prior to administration of the first dose of study treatment – note this may include measurements taken on the day of randomization. If a patient did not receive any dose of study treatment then the randomization date will be used.
Post-baseline efficacy	parasite count and temperature	The measurement closest to the target day/time will be used. In the event two measurements are taken equally apart, the first one will be used.
Post-baseline safety	Summary visit information (e.g. lab, ECG, etc.)	The measurement closest to the target day/time will be used. In the event two measurements are taken equally apart, the first one will be used.
Post-baseline safety	Notable abnormalities (e.g. lab, ECG, VS)	The most extreme measurement in the window will be used. Note this means a patient can have a notably high and notably low measurement within a window

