Blood chemistry - Point of Care device, Met Lac Panel	x	x	x	x	x	x
Hematological assessment - Point of Care device	x	x	x	x	x	x
Blood chemistry (INR and/or LDH) at local lab ⁹		x ⁹				
Electrocardiogram (ECG) ¹⁰					x	x
PK Collection ¹²	x	x				
Alpha 1-Acid glycoprotein (AAG) blood collection ¹³						
Urine analysis - local lab	x	x	x	x	x	x
CCI						
CCI						
CCI						
CCI						
CCI						
CCI						
CCI						
Pregnancy Test (serum) ⁷					s	
Body Height						
Body Weight					x	
Administration of IV therapy - Cipargamin (KAE609) Or Artesunate ¹⁸						
Administration of Oral Therapy (standard of care) ²⁰	x ²⁰	x ²⁰				
Contact IRT	x	x	x	x	x	As required
Adverse Events	Ongoing check					
Prior and concomitant medications ²¹	As required					

^x Assessment to be recorded in the clinical database or received electronically from a vendor

^s Assessment to be recorded only in source notes

¹ If participant is eligible for oral therapy and can be discharged per investigator opinion, discharge date will be noted. Earliest timepoint for discharge is 72 H (D4). However if a participant is not eligible to switch to oral therapy and needs to be on IV treatment then extend hospitalization and repeat all D4 assessments every 24 H till the participant is ready to take oral therapy.

² Screening and Randomization visit (D1, 0H) will occur on the same day within 3 hours of screening due to the acute need to treat severe malaria.

³ If participant is eligible for oral therapy then first dose of oral treatment (Coartem) should be given at 48 H (D3), else continue IV therapy.

⁴ D1 - 0 H is randomization visit.

⁵ Prior to start of any study procedure

⁶ Sample to be collected pre-dose

⁷ Pregnancy results must be confirmed negative before dosing. Refer [Section 8.4.6](#).

⁸ Refer modified WHO [Table 16-6](#) in [Section 16.4](#) for detailed assessments.

⁹ INR sample to be collected at pre-dose but only to be analyzed when participant is randomized. Follow-up post baseline samples should only be collected when required as per protocol during elevated lab parameters (refer [Section 16.1](#)) LDH to be collected at pre-dose and D8, and only to be analyzed when hemoglobin is decreased by $\geq 10\%$

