10.2.3 Special Hematology monitoring

Hematology parameters are closely monitored throughout the study to detect early and delayed hemolytic anemia.

Early Hemolytic anemia is defined as 10% or greater decrease in hemoglobin levels and an increase of LDH levels to $>390 \text{ U/L}$, or an increase of $\geq 10\%$ above baseline occurring up to Day 8 of the study.

Delayed hemolytic anemia might occur > 7 days after initiation of parenteral study drug (IV artesunate or IV cipargamin) during the study period. The event is characterized by a 10% or

greater decrease in hemoglobin levels accompanied by increase of LDH levels to >390 U/L, or an increase of $\geq 10\%$ compared to the values measured at Day 8 of the study.

Decrease in hemoglobin 10% or greater (compared to baseline up to Day 8 and compared to Day 8 values after until the end of study), must be always followed by LDH measurement for confirmation of hemolysis and requires close observation, follow-up monitoring and contributing factors are to be recorded on the appropriate CRFs.

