(ALT or AST) & TBL & ALP	ALT or AST >3xULN & TBL >2xULN & ALP <2xULN

Peak ALT and AST and peak TBL will be plotted using eDISH (evaluation of Drug Induced Serious Hepatotoxicity) method and Modified eDISH (mDISH) method, see Lin, et. al. (2012).

Listing of patients with the following laboratories will be provided:

- Serum creatinine increase 25 – 49% compared to baseline
- Serum creatinine increase $\geq 50\%$ compared to baseline
- New Plasma lactate > 4 mmol/l
- New dipstick proteinuria $\geq 1+$
- New dipstick hematuria $\geq 1+$

For urinalysis, frequency tables will be presented. Number and percent of patients in each category will be presented for each visit.

Laboratory measurements, which are recorded as below the assay detection limits, will be imputed as half of the detection limit; and those above the detection limit will be imputed as within the detection limit, for the summary statistics.

Analysis of Hemolysis

Early Hemolytic anemia is defined as 10% or greater decrease in hemoglobin levels and an increase of LDH levels to >390 U/L, or an increase of $\geq 10\%$ above baseline occurring up to Day 8 of the study.

Delayed hemolytic anemia occurs > 7 days after initiation of parenteral study drug (IV artesunate or IV cipargamin) during the study period. It is defined as 10% or greater decrease in hemoglobin levels and an increase of LDH levels to >390 U/L, or an increase of $\geq 10\%$ above Day 8 value. If Day 8 value is missing, use the closest value.

The number (and proportion) of patients with early hemolysis and number (and proportion) of patients with delayed hemolysis will be summarized by phase (Early or Delayed) and visit (Early: Days 1 to 3, Days 4 to 8, Days 1 to 8; Delayed: Days 9 to 15, Days ≥ 16 , \geq Day 9), cohort, and treatment group. For delayed hemolysis, visits after Day 8 will be reported.

Besides, number and percent of patients with decrease in hemoglobin $\geq 10\%$ (from baseline for early and from Day 8 for delayed) will be summarized by phase (Early or Delayed) and visit, cohort, and treatment group.

Analysis of Lactate

A shift table presenting a shift in lactate levels from baseline to each post-baseline visit will be provided by visit, cohort, and treatment group. The following categories will be used; ≤ 2 , > 2 - <4 , ≥ 4 mmol/l.

The percentage change from baseline in lactate level will be summarized by visit, cohort, and treatment group.

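### SAP Table 5-8 assigns every LDH result from Day 2 onwards to the Day 8 visit, which conflicts with the delayed-haemolysis analysis in SAP 2.8.2; the fallback for a missing Day 8 reference is also unsafe

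*SAP*

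**What the plan says.** **Windows.** In SAP 5.2.4, Table 5-8, the INR/LDH column has two entries: baseline (up to Day 1) and Day 8, defined as "Day 2 and above". Days 15, 22 and 29 are marked not applicable. Repeat and unscheduled visits "will be mapped for analysis purposes in the same way", and "The mapped visits will be used in the by visit analyses". Listings keep all collected data.

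**Endpoint.** Early and delayed haemolysis together form a secondary endpoint (Protocol Table 2-1, SAP Table 1-1). In SAP 2.8.2, "Delayed hemolytic anemia occurs > 7 days after initiation of parenteral study drug". It requires a haemoglobin fall of at least 10% with LDH either rising above 390 U/L or rising by at least 10% over the Day 8 value; if that value is missing, the closest value is used. Results are summarised by phase and visit. The early ranges are Days 1–3, 4–8 and 1–8; the delayed ranges are Days 9–15, 16 onwards and 9 onwards.

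**Sampling.** Protocol Table 8-1, footnote 9 (repeated in Table 8-2) has "LDH to be collected at pre-dose and D8, and only to be analyzed when hemoglobin is decreased by" at least 10%. Protocol 10.2.3 adds that any such fall, judged against Day 8 after that day and until the end of the study, "must be always followed by LDH measurement for confirmation of hemolysis". LDH after Day 8 is therefore triggered, not scheduled.

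**The concern.** The LDH results that decide delayed haemolysis are the triggered samples taken after Day 8, and Table 5-8 has no window for them. Protocol 12.5.2 and SAP 2.8.2 both summarise haemolysis by visit, so the instruction to use mapped visits applies on its face. Two programmers following different sections could report different delayed-haemolysis rates from the same data.

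Protocol 4.5 names delayed haemolysis as a potential risk of cipargamin and says it typically peaks at two to three weeks, a period in which LDH has no window of its own. SAP Table 2-13 lists it among the outputs for the interim assessment after Cohort 2 and the DMC review after Cohort 4, so an error could reach safety review.

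**Working it through.** **1. Reproducing Table 5-8.** The SAP 5.2.4 rule is: lower limit = "upper limit of prior applicable visit" + 1; upper limit = target + integer part of (next target − target)/2. For the last visit the text reads "No upper limit for Day 29 visit to include all assessments"; the table leaves the last scheduled visit of each assessment open-ended.

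| Assessment | Post-baseline targets | Windows from the rule | Matches table |
|---|---|---|---|
| ECG | 2, 3, 4, 29 | 2; 3; 4–16 (4 + int(25/2) = 16); ≥17 | yes |
| Body weight, Cohorts 1–3 | 2, 29 | 2–15 (2 + int(27/2) = 15); ≥16 | yes |
| AAG | 2, 3 | 2; ≥3 | yes |
| LDH | 8 | ≥2 | yes |

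The LDH window follows the rule correctly. The difficulty is that the rule uses scheduled visits only.

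**2. Applying the table to a delayed event.** Assumed values, for illustration: haemoglobin 10.0 g/dL on Day 8 and 8.5 on Day 20; LDH 300 U/L on Day 8 and 360 on Day 20.

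- By actual study day: haemoglobin 8.5/10.0 − 1 = −15%; LDH 360/300 − 1 = +20%. Delayed haemolysis is met.
- By Table 5-8, both LDH results are labelled Day 8. Table 5-10 then keeps either the result closest to target (300, so 360 is dropped) or, for notable abnormalities, the most extreme (360, relabelled Day 8). Under either rule no LDH remains after Day 8. A Day 20 result above 390 U/L would likewise be dropped or dated to Day 8.

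**3. The missing-reference rule, without Table 5-8.** Suppose the Day 8 LDH was not analysed and the only results are pre-dose (Day 1) and one triggered sample. The pre-dose sample is |1 − 8| = 7 days from Day 8. A triggered sample on any of Days 9–14 is 1 to 6 days away, so it is the closest value. For a Day 10 event the reference is the Day 10 result itself, and the change is 0%. If the pre-dose sample was not analysed either, a lone triggered sample on any day becomes its own reference. Only the ≥10% limb is affected.

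**4. Would extra windows suffice?** Adding Days 15, 22 and 29 as LDH visits under the same rule gives Day 8 = 2–11 (8 + int(7/2) = 11), Day 15 = 12–18, Day 22 = 19–25 and Day 29 = ≥26. The Day 8 window would still overlap the delayed phase, which starts on Day 9. Copying the haematology window from Table 5-9 (Days 8–11) has the same overlap. Any added windows must be split between Days 8 and 9.

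**The case against.** The strongest reply is that Table 5-8 was never meant to drive this endpoint. SAP 2.8.2 gives haemolysis its own day ranges, and these make sense only with actual study day. The Table 5-9 haematology windows of Days 8–11 and 12–18 straddle the 8/9 and 15/16 cuts, so mapped haemoglobin could not fill those rows either. Under Table 5-8 the Days 1–3 row would hold no post-baseline LDH at all. On this reading the endpoint can be derived.

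Much of this stands. A reader might infer from the table that delayed haemolysis cannot be derived correctly. The documents do not support that: the raw results are retained, and actual study day is the more plausible intention. But the SAP never states it, while it does say that mapped visits feed by-visit analyses. The two rules conflict, and nothing says which prevails.

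There are also backstops. SAP 2.8.2 summarises haemoglobin falls of at least 10% separately, without LDH, and SAP Table 2-5 includes a haemolytic-disorders query. These limit the risk of missing a safety signal, but neither yields the LDH-confirmed endpoint.

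Finally, footnote 9 does not confine the triggering haemoglobin fall to Day 8 or earlier, so it may already require the Day 8 sample to be run after a later fall. That reading is reasonable. The footnote does not say so outright, and it is silent on how long the sample is kept.

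**Conclusion.** The concern holds as a conflict between two SAP rules, together with a defect in the reference rule. If Table 5-8 is applied as written, no LDH after Day 8 remains and LDH-confirmed delayed events are dropped or mis-dated. If actual study day is used instead, that problem disappears, but the closest-value fallback can still make the event sample its own reference for the ≥10% limb.

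The number of events affected cannot be estimated. Protocol 4.5 cites delayed haemolysis in 7–27% of artesunate-treated severe malaria, and 0.07 × 116 = 8.1 and 0.27 × 116 = 31.3, so a reader might infer that 8 to 31 artesunate cases would be lost. The documents do not support that. These are hypothetical cases under definitions that the documents do not give, and the 116 includes 6 Cohort 1 participants with moderately severe malaria. Nothing indicates what share would be miscounted, since that depends on which rule is programmed, how often Day 8 LDH is absent, and which limb is met. The endpoint is descriptive, with no hypothesis test attached.

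**What to change.** 1. In SAP 5.2.4 and 2.8.2, state that haemolysis is derived from actual study day using the 2.8.2 ranges, split at Day 8/9, for both haemoglobin and LDH, and not from Table 5-8 mapped visits. Alternatively, add post-Day-8 LDH windows with that same split.
2. In SAP 2.8.2, define the delayed-phase LDH reference as the Day 8 sample or, if that is missing, the closest value before the event sample and never the event sample itself.
3. Make explicit that the collected Day 8 LDH sample is analysed, where still available, when a later haemoglobin fall of at least 10% occurs.

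The cost is a SAP edit and a few LDH assays on samples already collected. No extra visits or blood draws are needed.

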¹⁰ ECG's should be taken in triplicate within 5 min after resting for at least 10 min in the supine position. Last ECG should be taken 24 hours after final IV drug dose. Pre-dose ECG can be taken in less than 30 mins before first dosing and all post baseline ECG assessments (from D2 and D2 onwards) should be taken in less than 15 min post-dose.

¹¹ ECG assessment after drug administration.

¹² For all Cipargamin (KAE609) participants only. Rich PK collection with 1 ml blood. For scheduled time: Pre-dose samples (0, 24h, 48h, 72h) should be taken in less than 15 min before the dosing; Post-dose samples as following (Day 1: 2 min: + 1 min; 10 min: ± 2 min; >10 min - 3 h: ± 10 min; >3 - <24 h: ± 30 min; Day 2: 24h02m: + 1 min; >24h10 min - 27 h: ± 10 min; >27 - <48 h: ± 30 min; Day 3: 48h02m: + 1 min; >44h10 min - 52 h: ± 10 min; >52 - <72 h: ± 30 min) Exact time to be recorded for samples taken in follow-up period (Day 6 and Day 8).

¹³ For all Cipargamin (KAE609) participants only

CCI
[REDACTED]

¹⁸ Minimum and maximum duration of IV cipargamin will be 24 H (2 doses) and 48 H (3 doses). If cipargamin participants require IV therapy beyond 3 doses, refer rescue medication criteria ([Section 6.2.1](#)). Minimum and maximum duration of IV artesunate will be 24 H (3 doses) and 7 D (8 doses).

¹⁹ Day 1, 12 h dosing only for participants receiving IV artesunate

²⁰ First timepoint to switch from IV therapy to oral therapy is at 48 H. If participant is eligible, administer Coartem as per label. However, if participant is not able to tolerate oral therapy then continue with IV treatments and evaluate again at D4 and every 24h until participant receives oral therapy.

²¹ All medication administered or taken by the participants up to 72 hours prior first dose has to be reported as prior medication in the appropriate Case Report Forms.

²² EOS = End Of Study (D29) OR PSW = Premature Study Withdrawal (to be performed at last visit of the participant getting discontinued from the study)

Period	Screening	Hospitalization														Discharge day ¹	Follow-up						Unscheduled visit
Visit Name	Screening ²	D1 ²										D2				D3 ³	D4	D6	D8	D15	D22	D29 (EOS/PSW) ⁴	Unscheduled visit
Days	(-3 to 0 h)	1										2				3	4	6	8	15 ±1	22 ±2	29 ±2	-
Time (post-dose)	-	0h ⁵	2m	30m	1h	2h	4h	6h	12h	18h	24h	30h	36h	42h	48h	72h	120h	168h	336h	504h	672h	-	
Inclusion / Exclusion criteria	X																						
Informed consent ⁶	X																						

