2.1.1 General definitions

Study treatment: IV Cipargamin and IV artesunate are randomized treatments. Coartem tablets (20/120 mg and 80/480 mg tablets) are used for oral therapy following the IV therapy for all patients. Coartem is not an investigational treatment and will not be presented in the treatment group name. Treatment group name will be used in statistical analyses and outputs. These treatment groups will be used as the column headers in the CSR outputs.

For example, the initial treatment groups in Cohort 1-2 will be displayed as:

- IV Cipargamin 20mg

- IV Cipargamin 40mg
- IV Artesunate

As per study design, other IV cipargamin dose levels may also be used. Treatment groups for each of the combinations will be used accordingly. For Cohorts 3 to 5, the IV Cipargamin dose level will be the equivalent dose level intended for patients ≥ 35 kg.

Baseline: The last measurement made prior to administration of the first dose of study treatment. Note: this may include measurements taken on the day of randomization (e.g. lab, ECG, vitals).

Study day: Study day will be calculated with respect to the first dose of study treatment. If a patient did not receive any dose of study treatment then the randomization date will be used as the date of first dose of study treatment. The first day of administration of study treatment (first dose) is defined as Day 1. Day -1 will be the day before Day 1. Day 0 does not exist. For some variables, assessments are collected more than once a day during first 3 days. Study day calculation for such assessments is based on the treatment start date and time.

For the assessments that are performed more than once a day: Study day = Integer (datetime of assessment – datetime of first dose of study treatment)/(60*60*24) + 1.

For assessments that are performed once for a day: Study day = date of assessment – date of first dose of study treatment + 1.

For assessments collected prior to Day 1, study day = date of assessment - date of first dose of study treatment.

Body temperature: Body temperature is measured using different routes (oral/rectal/tympanic/axillary), which will lead to variations in the readings. Therefore, all the temperature readings will be standardized with respect to tympanic equivalent as follows for the reporting purpose:

Body temperature (oral/tympanic/rectal equivalent) = Axillary temperature + 0.5°C.

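### SAP Table 5-9 separates pre-dose from post-dose PK samples at 24 h 1 min and 48 h 1 min after the first dose, so small timing deviations of doses 2 and 3 can mislabel troughs and peaks in the Cohort 1-3 concentration summaries

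*SAP*

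**What the plan says.** - **Time origin.** For assessments made several times a day, SAP 2.1.1 states: "Study day calculation for such assessments is based on the treatment start date and time". SAP 5.2.4 says Table 5-9 "describes the analysis windows mapping to visits based on study day and time". Neither place refers to the time of dose 2 or dose 3.
- **Windows, Cohorts 1-3.** Table 5-9 has a dedicated PK column. The 24 h pre-dose window is ">18 – 24 hrs 1 min" and the 24 h 2 min window is ">24 hrs 1 min-24 hrs 31 min". At 48 h the pre-dose window also ends at 48 h 1 min, followed by ">48 hrs 1 min – 48 hrs 31 min".
- **Windows, Cohorts 4-5.** The 24 h window is ">12.5 hrs – 36 hrs". The protocol schedules no post-dose PK sample at 24 h or 48 h for these cohorts.
- **Collection.** Protocol Table 8-1, footnote 12, ties sampling to the dose: "Pre-dose samples (0, 24h, 48h, 72h) should be taken in less than 15 min before the dosing". The 2-minute samples may be taken up to 1 minute later than nominal. Protocol Table 6-2 schedules doses at 0, 24 and 48 h and gives no tolerance in minutes.
- **Several samples in one window.** Table 5-10 says: "The measurement closest to the target day/time will be used". Its rows name parasite count, temperature and safety data, not PK.
- **Use.** SAP 5.2.4 sends mapped visits into by-visit analyses. SAP 2.9 summarises concentrations by visit. Table 2-13 lists concentration among the outputs for the interim assessment after Cohort 2.

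**The concern.** The sample before and the sample after an intravenous bolus are minutes apart but measure opposite ends of the concentration curve. The SAP separates them with a fixed clock boundary 1 minute from each target, while both samples move with the actual dose. A dose given slightly off schedule carries one of them across the boundary, and a post-bolus value is then summarised as a trough or a trough as a post-bolus value.

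At stake are the descriptive concentration tables at 24 h and 48 h for the cipargamin arms in Cohorts 1-3. These arms have 6, 14 and 38 participants, so a few misplaced values can distort means, geometric means and coefficients of variation.

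**Working it through.** **1. Reproducing the cut-offs.** SAP 5.2.4 places each upper limit halfway to the next target. Between 24 h 0 min and 24 h 2 min the midpoint is 24 h 1 min. Between 24 h 2 min and 25 h it is (2 + 60)/2 = 31, that is 24 h 31 min. All 15 cut-offs for Cohorts 1-3 and all 3 for Cohorts 4-5 reproduce. The boundaries follow the SAP's own rule and are not misprints.

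**2. Set-up.** Let the later dose be d minutes off 24 h (negative if early). In minutes relative to 24 h:
- pre-dose sample: d − u, with u from 0 to 15 (protocol limit);
- 2-minute sample: d + 2 + v, with v from 0 to 1 (protocol limit);
- trough window up to 1; post-dose window above 1 and up to 31.

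**3. Dose early.** The 2-minute sample falls in the trough window when d + 2 + v ≤ 1, that is d ≤ −1 − v. This can begin just beyond 1 minute early and is certain from 2 minutes early. That sample is also nearer to 24 h than the true trough, so a closest-to-target rule would keep it. The post-dose slot loses its own sample and is empty. Only when the dose is more than 19 minutes early can the 1-hour sample (tolerance ±10 minutes) drop into that slot, since 60 − 10 − 19 = 31.

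**4. Dose late.** The pre-dose sample falls in the post-dose window when d − u > 1. With u uniform over 0 to 15, the probability is (d − 1)/15 for d between 1 and 16:

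| Minutes late | Pre-dose sample in post-dose window |
|---|---|
| 3 | 2/15 = 13% |
| 5 | 4/15 = 27% |
| 10 | 9/15 = 60% |
| 15 | 14/15 = 93% |
| 16 | 100% |

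Where this happens the trough slot is empty and, under a closest-to-target rule, the trough is reported as the 24 h 2 min value. From 29 minutes late the 2-minute sample itself moves to the 25 h window.

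**5. No exchange.** The windows keep time order, so both samples can share a window but cannot trade places. Simulation gave 0% two-way exchanges. The results at 48 h are the same.

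**6. Illustrative size.** The documents give no spread for dose times, so this step is assumption throughout: d normal around schedule, u and v uniform, closest-to-target applied to PK. As shares of all participants, simulation gives a peak in the trough slot for 38% and a trough in the peak slot for 10% at SD 5 minutes, and 46% and 29% at SD 15 minutes. As shares of filled slots:
- SD 5: 38/(100 − 10) = 42% of trough slots hold a peak; 10/(100 − 38) = 16% of peak slots hold a trough. Unrounded inputs give about 43% and 17%.
- SD 15: 46/(100 − 29) = 65%; 29/(100 − 46) = 54%. The 54% leaves out post-dose slots filled by a stray 1-hour sample.

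If doses run only late (half-normal, SD 5), no trough slot holds a peak and about 20% of peak slots hold a trough.

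**The case against.** The strongest reply is that two links are inferred. Table 5-9 does not itself say that its hours run from the first dose; the SAP 2.1.1 definition concerns study day. SAP 5.2.4 also opens conditionally, and Protocol 12.5.3 summarises concentrations by visit or sampling time point, which would fit nominal labels. Table 5-10 does not name PK. These points stand as caveats. Against the first, Table 5-9 has PK columns with minute-level cut-offs, and no dose other than the first is given as an origin. If Table 5-10 does not apply to PK, the SAP has no rule for two PK samples in one window, which is a gap in itself.

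The second reply is about reach, and it limits the point. A reader might infer that troughs and peaks are swapped, or that any deviation of a few minutes mislabels them. The windows make an exchange impossible, and a slightly late dose does harm only if the pre-dose sample was drawn after the boundary. A reader might also infer that Cmax, AUC or the exposure checks behind dose decisions are corrupted. Protocol 8.5.1 derives non-compartmental parameters from actual sampling times, Protocol 4.2 bases predicted exposures on population PK or PBPK models, and nothing links the pharmacokineticist's exposure review in Protocol 4.4 to Table 5-9. Listings show all collected data, though they do not correct the tables.

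**Conclusion.** The point holds in limited form. Read with time running from the first dose, Table 5-9 guarantees correct trough and post-dose labels only when the later dose is within about 1 minute of schedule. The thresholds (certain from 2 minutes early, certain from 16 minutes late) follow from the SAP boundaries and protocol sampling limits alone. The intermediate late-dose percentages need a uniform draw time. The filled-slot shares need an assumed spread of dose times, so they illustrate sensitivity and do not forecast an error rate. Displacement of the correct sample also needs the Table 5-10 rule to apply to PK.

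The consequence is confined to by-visit concentration summaries at 24 h and 48 h in the cipargamin arms of Cohorts 1-3, including the concentration output at the interim assessment after Cohort 2. Cohorts 4-5, the non-compartmental parameters and the efficacy results are not touched. The correction is still worth making, because the tables could otherwise present post-bolus values as troughs.

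**What to change.** For PK in Cohorts 1-3, amend SAP 5.2.4 as follows:

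- Assign samples around 24 h and 48 h by time relative to the most recent recorded dose, or by the nominal scheduled time point, in place of the Table 5-9 clock windows.
- Require that a sample summarised as pre-dose precedes that dose, and that one summarised as 2-minute post-dose follows it.
- State which sample is used when several PK samples fall in one window, either by naming PK in Table 5-10 or by a separate rule.

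Mapped this way, a pre-dose sample (15 to 0 minutes before) and a 2-minute sample (2 to 3 minutes after) are labelled correctly whatever the deviation of the dose. The cost is SAP wording and programming, with no new data, provided the clock times of doses 2 and 3 are recorded. The documents make this plausible but do not state it, so it should be confirmed first.
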